6.1.2. Sorafenib group (monotherapy group) (Table 2)

Sorafenib will be administered continuously at a dose of 400 mg twice daily for 28 days from day 1 to day 28. This 4-week period constitutes one cycle, and cycles will be repeated until discontinuation of the protocol treatment.

The first cycle of treatment will be started within 28 days of randomization. If an adverse event is observed during treatment with sorafenib, treatment will be interrupted or the dose will be reduced as appropriate in accordance with **6.3.2. Criteria for adjusting the sorafenib dose (dose interruption and reduction)**. After the protocol treatment is discontinued, appropriate treatment as described in **Section 6.5 Post-trial Treatment** will be performed.

Table 1 Treatment schedule (low-dose FP plus sorafenib combination therapy group)

*Patients must be off sorafenib for 2 days before and 7 days after reservoir placement.

	1	2	3	4	5	6	7	8	9	10	11	12	13	14
Sorafenib	↓	↓	↓	↓	↓	↓	↓	↓	↓	↓	↓	↓	↓	↓
CDDP	↓							↓						
5-FU	←————→							←————→						

	15	16	17	18	19	20	21	22	23	24	25	26	27	28
Sorafenib	↓	↓	↓	↓	↓	↓	↓	↓	↓	↓	↓	↓	↓	↓
CDDP														
5-FU														

Table 2 Treatment schedule (sorafenib monotherapy group)

	1	2	3	4	5	6	7	8	9	10	11	12	13	14
sorafenib	↓	↓	↓	↓	↓	↓	↓	↓	↓	↓	↓	↓	↓	↓

	15	16	17	18	19	20	21	22	23	24	25	26	27	28
sorafenib	↓	↓	↓	↓	↓	↓	↓	↓	↓	↓	↓	↓	↓	↓

6.2. Criteria for Discontinuation of the Protocol Treatment

In general, in situations such as the following, the protocol treatment will be discontinued, a note to that effect will promptly be written on the patient’s medical records, and a Treatment Completion Report will be faxed to the data center.*

- 1) Progressive disease
 - a) Progressive disease (PD) as defined by the modified RECIST criteria is confirmed by imaging**
 - b) Worsening of general condition indicates a lack of clinical response to treatment
- 2) Patient cannot continue the study due to an adverse event
 - a) Patient cannot resume sorafenib after 8 weeks of interruption due to an

adverse event

b) Patient cannot start the next cycle of treatment within 8 weeks after completing the previous cycle due to an adverse event

c) An adverse event that meets the criteria for dose reduction occurs after the dose was already reduced to the lowest level

(Reducing the dose to below the lowest level in the dose reduction criteria stipulated in the protocol will be considered discontinuation of the protocol treatment, and all treatment after that point will be considered post-trial treatment.)

3) Hepatic arterial infusion chemotherapy becomes technically infeasible

4) Patient requests to discontinue the study

5) Patient can no longer make continuous visits due to moving or changing doctors

6) Death

7) An investigator determines that discontinuation is necessary for any other reason

8) The patient shows a CR

***Notes regarding discontinuation of the protocol treatment**

The protocol treatment should be continued for as long as possible by reducing doses and interrupting treatment as appropriate. If discontinuation is being considered after a dose reduction or during treatment interruption, the study coordinator or study chair should be promptly notified using the designated fax form. Whether to discontinue the protocol treatment will be determined upon discussion with the study chair. It is particularly important to promptly consult the study chair when considering discontinuation for a patient who does not meet the above criteria for discontinuation of the protocol treatment. However, it is acceptable to not follow this procedure if emergency discontinuation is required for safety reasons.

Contact information:

Study chair: [name], Department of Gastroenterology and Hepatology, Kindai University Faculty of Medicine

[contact] ([name])

[contact]

E-mail: [contact]

Study coordinator: [name], Department of Gastroenterology and Hepatology, Kindai University Faculty of Medicine

[contact] ([name])

[contact]

E-mail: [contact]

**The protocol treatment should generally be discontinued if the patient shows PD according to the modified RECIST criteria during the protocol treatment period. However, continuation of the protocol treatment is allowed if the investigator determines that the patient is responding clinically to the protocol treatment. It should be noted that observation of a new hepatic lesion is not considered PD in this study, and protocol treatment should be continued in these patients.

***The protocol treatment should be discontinued if the patient shows a CR according to the modified RECIST criteria. If recurrence is detected, appropriate treatment will be provided at that time. Treatment during this time will follow Section 6.5. Post-trial Treatment.

6.3. Criteria for Treatment Adjustment

6.3.1. Criteria for starting the next cycle (for both groups)

The next cycle will be started if the investigator confirms the following criteria are met within 1 week before the scheduled start date. If any of these criteria are not met, the interval to the next cycle will be extended and the next cycle will be started as soon as the criteria are met. The next cycle cannot be started if the patient is off sorafenib. The start date of the next cycle can be extended for up to 8 weeks from the end of the previous cycle. If the criteria for starting the next cycle are still not met after that period, the protocol treatment will be discontinued.

- 1) Neutrophil count $\geq 1,000/\mu\text{L}$
- 2) Platelet count $\geq 50,000/\mu\text{L}$
- 3) Total bilirubin ≤ 2 mg/dL
- 4) ALT and AST ≤ 6 times the institutional upper limit of normal
- 5) Serum creatinine ≤ 1.5 times the institutional upper limit of normal
- 6) Amylase ≤ 2 times the institutional upper limit of normal

6.3.2. Criteria for adjusting the sorafenib dose (dose interruption and reduction)

The dose of sorafenib will be adjusted (by interruption or reduction) in the event of clinically significant hematological or non-hematological toxicity attributed to sorafenib. When grading events according to the Japanese translation of the CTCAE v4.0, the grade whose definition most closely matches the event will be assigned. When grading events, investigators will consider not only the fact that the patient received a certain treatment, but also whether that treatment was indicated for the patient's condition. However, they will also consider whether it is possible to continue treatment with sorafenib by increasing the frequency of tests. The following criteria will be followed for each dose reduction level.

Table 3 Dose reduction method

Standard dose	Dose level 1	Dose level 2	Dose level 3
400 mg twice daily	400 mg once daily	400 mg every other day	200 mg every other day
Two 200 mg tablets of sorafenib per dose Twice daily (morning and evening)	Two 200 mg tablets of sorafenib per dose Once daily (morning)	Two 200 mg tablets of sorafenib per dose Once every other day (morning)	One 200 mg tablet of sorafenib per dose Once every other day (morning)

When an adverse event occurs, the dose will be reduced as outlined above. When the adverse event resolves, treatment will be resumed whenever possible, but generally at a reduced dose. After that, the dose may be increased up to 400 mg twice daily at the discretion of the investigator or subinvestigator. When the dose is increased, it will be increased by one level at a time. The protocol treatment will be discontinued if the dose is reduced below level 3.

Table 4 Criteria for adjusting the sorafenib dose for hypertension

Grade	Feasibility of continuing treatment	Dose adjustment
Grade 1	Consider increasing frequency of blood pressure measurements	No change
Grade 2 asymptomatic increase in diastolic blood pressure to < 100 mmHg	Start treatment with an antihypertensive. Continue treatment with sorafenib. If previously untreated, start treatment with one antihypertensive. If patient is already using an antihypertensive, increase the dose of the antihypertensive they are using.	No change

Level 2: Fluorouracil 170 mg/m², cisplatin 10 mg/m²

(It is also acceptable to interrupt infusions of cisplatin alone without reducing the fluorouracil dose if the adverse event is caused by renal dysfunction)

6.4. Concomitant Treatment and Supportive Care

All concomitant medications will be documented in medical records. (Including start dates, end dates, and indications.)

6.4.1. Permitted concomitant treatments and supportive care

The following concomitant treatments and supportive care may be provided if necessary.

- 1) Patients may receive non-targeted therapy for the primary disease (e.g., *kampo* medicine and acupuncture) or eat foods fortified with vitamins/minerals if the investigator or subinvestigator determines the treatment or food will not interfere with or influence evaluation of study results.
- 2) Palliative care or supportive care may be provided for the primary disease as long as prohibited drugs are not used.
- 3) Palliative radiotherapy may be performed if the cancer is not recurrent or progressing, and target lesions are not in the irradiated area.
- 4) Analgesics
- 5) Antiemetics
- 6) Antihypertensives
- 7) Topical medication to treat hand-and-foot skin reaction

Patients using drugs known to be metabolized by the liver and drugs with a narrow therapeutic range, like digoxin, will be monitored carefully for adverse reactions.

6.4.2. Prohibited concomitant treatments and supportive care

Patients may not receive the following treatments during the protocol treatment period.

- 1) *Shosaikoto* (*kampo* medicine)
- 2) Drugs (e.g., rifampicin) or foods (e.g., St. John's wort) that induce CYP3A4
- 3) Antitumor drugs and treatments believed to act on tumors that are currently approved, in development, or under investigation, as well as radiotherapy and surgery
(However, palliative radiotherapy is allowed.)
- 4) Cytokine formulations including interferons
- 5) Bone marrow and hematopoietic stem cell transplantation

- 6) Local therapy for hepatocellular carcinoma (resection, RFA, or TACE)

6.5. Post-trial Treatment

Treatments for hepatocellular carcinoma not described in this protocol will not be performed until criteria for discontinuation of protocol treatment are met. Post-trial treatment for after the protocol treatment is concluded is not defined in this protocol. If the cancer is downstaged, local therapy (e.g., resection, RFA, or TACE) can be performed at the investigator's discretion.

However, **post-trial treatment of the sorafenib monotherapy group with low-dose FP and sorafenib, or post-trial treatment of either group with TACE and sorafenib, is prohibited because these treatments are currently only approved for use in clinical studies.**

The protocol treatment should generally be discontinued if the patient shows PD according to the modified RECIST criteria during the protocol treatment period. However, continuation of the protocol treatment is allowed if the investigator determines that the patient is clinically responding to the protocol treatment. Continuation of treatment in this situation will not be considered post-trial treatment.

Reducing the dose to below the lowest level in the dose reduction criteria stipulated in the protocol will be considered to constitute discontinuation of the protocol treatment, and all treatment after that point will be considered post-trial treatment.

7. EXPECTED ADVERSE EVENTS

An adverse event (AE) is defined as any undesirable medical event that occurs in a patient receiving the study drug (excluding worsening of the primary disease). These events may or may not have a clear causal relationship with the study drug. Essentially, an adverse event is any undesirable or unintended sign (including abnormal laboratory test values), symptom, or condition that arises in a patient receiving the study drug, regardless of whether the event has a causal relationship with the study drug. In this study, adverse events that satisfy the above definition will be identified and recorded on case report forms.

If the grade according to the Japanese translation of CTCAE v4.0 worsens, the change will be reported as an adverse event on a case report form. This may also apply to changes within reference ranges or grades if the site investigator believes the event merits clinical consideration (including changes in test values).

The causality of adverse events will also be recorded on case report forms. The Japanese

translation of CTCAE v4.0 will be used for coding adverse events.

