7.2. Adverse Events Caused by Catheters and Reservoirs

Events such as bleeding associated with arterial puncture, hematoma, intimal injury, neuropathy, aneurysm, arteriovenous fistula, infection, pain (all rare), blood vessel perforation by the catheter/guidewire (rare), spasms and obstruction (rare), infection and pain (rare), nausea/vomiting (20%), vagal response (rare), shock caused by iodine contrast medium (very rare), and foreign matter left in blood vessels after equipment breakage (very rare) are anticipated to occur during catheterization before the start of the study. These events may also occur later. Events such as hemorrhage, hematoma, intimal injury, neuropathy, infection, and pain are also anticipated with reservoir placement.

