10.1. Adverse Events Subject to Mandatory Reporting

10.1.1. Adverse Events Subject to Expedited Reporting

Adverse events that meet any of the below criteria are subject to expedited reporting.

1) All deaths that occur during the protocol treatment or within 30 days* of the last day of the protocol treatment

This applies regardless of causality. In the case of patients who discontinued the protocol treatment, all deaths within 30 days of the last day of the protocol treatment are subject to expedited reporting, even if the patient already started post-trial treatment.

*: Here, “30 days” refers to 30 days beginning from the day after the last day of the protocol treatment, with the last day of treatment considered as day 0.

** : Deaths of patients who did not receive the protocol treatment after enrollment are not subject to expedited reporting. However, evaluation of eligibility at enrollment and other necessary evaluations will be made as appropriate through regular monitoring.

2) Unexpected grade 4 adverse events

Grade 4 adverse events that are not listed on the package inserts for the study drugs and are judged to have a causal relationship (definite, probable, or possible) with the protocol treatment are subject to expedited reporting.

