11.4. Patients Included in Analysis

Analysis populations

Safety evaluation: Randomized patients will be included in the safety evaluation.

Efficacy evaluation: The full analysis set (FAS) defined in Section 11.3 will be used.

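### Harm from reservoir placement before the first dose of any study drug falls outside the adverse event definition, and only the combination arm has that step

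*Protocol*

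**What the plan says.** Section 7 sets the limit: "An adverse event (AE) is defined as any undesirable medical event that occurs in a patient receiving the study drug". It then states that "adverse events that satisfy the above definition will be identified and recorded on case report forms". Section 7.2, headed as adverse events caused by catheters and reservoirs, lists bleeding, vessel injury, infection, contrast shock and others that "are anticipated to occur during catheterization before the start of the study". It adds: "These events may also occur later".

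Section 6.1.1 gives the combination arm up to 28 days from randomisation to start the first cycle. It permits sorafenib ahead of the infusions and sets off-drug days around reservoir placement. Section 6.1.2 gives monotherapy the same 28-day limit and no placement step.

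Section 7.4 asks investigators to watch for adverse events over the whole study, and to record the causal relationship to each study drug. On deaths, the expedited rule in Section 10.1.1 covers protocol treatment and the 30 days after its last day, regardless of cause. A note then says: "Deaths of patients who did not receive the protocol treatment after enrollment are not subject to expedited reporting". Those deaths are left to regular monitoring as appropriate. The regular report of later deaths in Section 10.1.2 is also counted from the last day of protocol treatment. Section 11.4 states: "Safety evaluation: Randomized patients will be included in the safety evaluation".

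**The concern.** The trial tests the addition of an invasive strategy to an oral drug, and safety is one of the endpoints to be compared. The procedure that makes the infusion possible belongs to that strategy, and its harm should be collected as completely as harm from the drugs. As written, collection begins with the first dose, whereas the procedure can come earlier. The gap is one-sided because monotherapy patients have no placement. It also cannot be repaired afterwards: an event that was never put on the form is not available to any analysis plan.

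**Working it through.** The protocol states no figure on this point, so the check sets the sections side by side and then gives one calculation for scale.

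**Case A: placement after randomisation, no study drug yet given.**
- Adverse event definition (Section 7): not met, since the patient is not receiving a study drug. Recording is tied to that definition.
- Surveillance over the whole study (Section 7.4): does not close the gap, because what is watched for is adverse events as Section 7 defines them.
- Scheduled assessments: Section 8.1 covers the period before enrolment and Section 8.2.1 the weeks of the first cycle. Nothing is scheduled between them.
- Causality (Section 7.4): the item refers to each drug. A catheter injury in an undosed patient has no entry that fits.
- Death without any dose: exempt from expedited reporting (Section 10.1.1). It also has no date from which the Section 10.1.2 rule for deaths could count.
- Safety population (Section 11.4): the patient is in the denominator, but the event need not have been recorded for the numerator.

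**Case B: sorafenib given first, then placement.** A death falls during protocol treatment or within 30 days of its last day, and is reportable whatever its cause. Other harm is arguably within the definition, although the required off-drug days leave it unclear whether the patient counts as receiving the drug.

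**Case C: complication after the first dose.** Within the definition.

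The defect is therefore confined to Case A, with some ambiguity in Case B.

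**Scale.** Inputs: 95 patients per arm (Section 12.1), and 20% nausea/vomiting with catheterisation, the only numeric rate in Section 7.2. Assumptions: every combination patient has a placement after randomisation, and a share s of placements comes before any study drug. The protocol does not give s.

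Events expected at catheterisation = 0.20 × 95 = 19.

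Events outside the definition = 19 × s:
- s = 25%: 4.75, about 5
- s = 50%: 9.5, about 10
- s = 100%: 19

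Monotherapy: 0, since there is no placement. For the graver complications Section 7.2 says rare or very rare, or gives no frequency, so no count can be derived for them.

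**The case against.** The best reply is that the protocol does not set out to ignore these events. Section 7.2 calls them adverse events in its heading. Section 7.4 asks for surveillance throughout the study. Table 10 defines causality against the protocol treatment, and the catheter instructions stand under the protocol treatment heading in Section 6.1. A sensible investigator might well record a placement injury. This stands in part: the text contradicts itself rather than plainly excluding the events. But what goes on the form is tied to the narrower definition, so sites can differ in what they record.

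Three stronger readings are tempting, and the documents do not support them.

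1. A reader might infer that all reservoir harm goes uncounted. Cases B and C show otherwise.
2. A reader might infer that the monitoring committee never hears of an undosed death. The exemption removes only expedited reporting. Section 10.1.1 refers these patients to regular monitoring, and Section 14.1 sends the monitoring reports to the committee. That route is slower and discretionary. It may also be incomplete: Section 14.2 monitors survival in all eligible patients, while the population definitions count those unable to start treatment among the ineligible. But it exists.
3. A reader might size the gap by applying the planning death rate to the 28-day window. That gives background mortality, not harm from placement. Any difference between arms would come from assumed start delays, since both arms have the same limit.

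Two neighbouring matters are separate: the loss of untreated patients from the full analysis set used for efficacy, and the effect of untreated patients on safety denominators. Neither shows that placement harm goes unrecorded.

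**Conclusion.** The point holds for placement between randomisation and the first dose of any study drug. In that window the definition in Section 7 contradicts Section 7.2, the causality item has no place for the procedure, and the death of a patient who is never dosed is not reported promptly. The omission can occur only in the combination arm and would make it look safer.

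On the one rate available, about 5 to 19 nausea/vomiting events could fall outside the definition if 25% to 100% of placements precede study drug. That share is assumed, and the events counted are mild. The number of serious or fatal placement events cannot be estimated from the protocol. Section 12.2 reports that many patients could not start treatment, so an undosed group exists, but it gives neither a number nor a split by arm. The point also assumes that placement follows randomisation, as it must where the reservoir is placed because of the assignment.

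This should be corrected, but it does not by itself undermine the trial's main conclusion.

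**What to change.** Reconcile Sections 7, 7.2, 7.4, 10.1.1 and 10.1.2:

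- **Sections 7 and 7.4:** collect adverse events from randomisation in both arms, whether or not study drug has been given.
- **Section 7.4 and the case report form:** add a causality item for catheter or reservoir placement beside the items for each drug.
- **Section 10.1.1:** make any death within 30 days of an attempted placement subject to expedited reporting, even if no study drug was given. Deleting the exemption altogether would be the wrong repair. It would leave no reporting window for patients with neither drug nor placement, and would bring in undosed monotherapy deaths unrelated to the procedure.
- **Section 10.1.2:** align the regular reports so that a later death suspected to result from placement has a date to count from.
- **Safety tables:** list separately the patients who had neither study drug nor attempted placement.

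The cost is amended wording, one added form item, slightly more adverse event recording between randomisation and first dose, and a few extra reports. No treatment rule changes. Events already missed in enrolled patients could be sought only by going back to site records.

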7.1. Adverse Events Expected with Each Drug

The appended latest versions of the package inserts for each drug should be referenced for adverse drug reactions anticipated with each drug.

7.1.1. Adverse Events Caused by Sorafenib

Below is an excerpt from the package insert.

Most common adverse reactions to sorafenib

Adverse reactions were observed in 141 of 145 patients in a Japanese phase II study in renal cell carcinoma and a Japanese phase I study in hepatocellular carcinoma. The most common adverse reactions (number of patients, incidence) included increased lipases (85 patients, 58.6%), hand and foot syndrome (80 patients, 55.2%), increased amylase (59 patients, 40.7%), rash (59 patients, 40.7%), hair loss (53 patients, 36.6%), diarrhea (51 patients, 35.2%), hypertension (40 patients, 27.6%), fatigue (23 patients, 15.9%), anorexia (21 patients, 14.5%), pruritus (21 patients, 14.5%), weight loss (18 patients, 12.4%), hoarseness (16 patients, 11.0%), and increased AST (GOT) (15 patients, 10.3%).

Clinically significant adverse reactions to sorafenib

- 1) Hand and foot syndrome ($\geq 10\%$) and exfoliative dermatitis (1-10%): Hand and foot syndrome and exfoliative dermatitis may occur. If skin symptoms appear, consider symptomatic treatment, dose reduction, or interruption or discontinuation of sorafenib.
- 2) Stevens-Johnson syndrome (frequency unknown) and erythema multiforme (0.1-less than 1%): Stevens-Johnson syndrome and erythema multiforme may occur. Monitor patients carefully, discontinue treatment, and take appropriate therapeutic measures if Stevens-Johnson syndrome or erythema multiforme is suspected.
- 3) Hypertensive crisis (0.1-less than 1%): Hypertensive crisis may occur. Carefully monitor changes in blood pressure during use. Discontinue sorafenib and take appropriate therapeutic measures if hypertensive crisis occurs.
- 4) Reversible posterior leukoencephalopathy (0.1-less than 1%): Reversible posterior leukoencephalopathy may occur. Monitor patients carefully, discontinue sorafenib, and take appropriate therapeutic measures (e.g., blood pressure control and anticonvulsants) if reversible posterior leukoencephalopathy is suspected.
- 5) Gastrointestinal perforation (0.1-less than 1%): Gastrointestinal perforation may occur, and deaths from this reaction have been reported. Discontinue sorafenib and take appropriate therapeutic measures if gastrointestinal perforation is suspected.
- 6) Hemorrhage (gastrointestinal hemorrhage, pulmonary hemorrhage, cerebral hemorrhage, oropharyngeal hemorrhage, epistaxis, subungual hemorrhage, and hematoma) ($\geq 10\%$): Severe hemorrhage such as gastrointestinal hemorrhage, pulmonary hemorrhage, and

cerebral hemorrhage may occur, and deaths from this reaction have been reported. Monitor patients carefully during treatment, discontinue sorafenib, and take appropriate therapeutic measures if severe hemorrhage is suspected.

7) Myocardial ischemia/infarction (0.1-less than 1%): Myocardial ischemia/infarction may occur, and deaths from this reaction have been reported. Monitor patients carefully, discontinue sorafenib, and take appropriate therapeutic measures if any abnormalities are observed.

8) Congestive heart failure (0.1-less than 1%): Congestive heart failure may occur, and deaths from this reaction have been reported. Monitor patients carefully, discontinue sorafenib, and take appropriate therapeutic measures if any abnormalities are observed.

9) Liver dysfunction/jaundice (0.1-less than 1%), hepatic failure (frequency unknown), hepatic encephalopathy (frequency unknown): Liver dysfunction, jaundice, hepatic failure, and hepatic encephalopathy accompanied by elevated AST (GOT) and ALT (GPT) may occur. Monitor patients carefully, reduce the dose of sorafenib, interrupt treatment or discontinue sorafenib, and take appropriate therapeutic measures if any abnormalities are observed. Hepatic encephalopathy has primarily been reported in patients with hepatocellular carcinoma or cirrhosis of the liver. As such, patients in these groups should be carefully monitored for clinical symptoms such as impaired consciousness.

10) Pancreatitis (0.1-less than 1%): Pancreatitis may occur. Monitor patients carefully, interrupt or discontinue treatment with sorafenib, and take appropriate therapeutic measures if symptoms suggestive of pancreatitis (e.g., abdominal pain) or persistent elevation of pancreatic enzymes is observed.

11) Acute lung injury and interstitial lung disease (frequency unknown): Acute lung injury and interstitial lung disease may occur. Monitor patients carefully for clinical symptoms such as dyspnea, fever, and cough, and promptly take a chest X-ray if any abnormalities are observed. Discontinue sorafenib and take appropriate therapeutic measures (e.g., treatment with corticosteroids) if acute lung injury or interstitial lung disease is suspected.

12) Leukopenia, neutropenia, lymphopenia, thrombocytopenia, and anemia (frequency unknown): Leukopenia, neutropenia, lymphopenia, thrombocytopenia, and anemia may occur. Monitor patients carefully, and reduce the dose of sorafenib, interrupt treatment or discontinue sorafenib, and take appropriate therapeutic measures if any abnormalities are observed.

13) Renal failure (frequency unknown): Renal failure may occur. Monitor patients carefully, discontinue sorafenib, and take appropriate therapeutic measures if any abnormalities are observed.

